6.1.2 Secondary outcomes

1. Vaccination uptake in patients after 3- and 9-months follow-up (>90 and >270 days). This will be measured as the number (percent) of relevant SNOMED codes in eligible patients identified during the period.
2. Mean vaccination rate after 3-, 6- and 9-months follow-up. This will be measured as the number of patients vaccinated divided by the follow-up time. Time is defined as time from randomisation until the earliest of vaccination, leaving the GP, withdrawal the consent of use of data, or death.
3. Acceptability of the intervention
 - a. To patients: Proportion of patients randomised to the intervention who engage with the PET and / or linked patient resources, as determined by user statistics logged on the software for
 - i. The SMS messaging tool (number of SMS sent)
 - ii. Number (percent) of patients who view the linked patient awareness resources
 - iii. Usage of the patient work list tool
 - b. To staff: Number and proportion of eligible patients randomised to the intervention processed using the patient work list tool
4. Feasibility of the intervention and randomisation
 - a. Number and proportion of eligible patients randomised
 - b. Clinical capacity: number of slots available for vaccination bookings for each GP surgery and each day, by appointment time
5. Feasibility of the study design for a subsequent trial

- a. Number and proportion of patients with all inclusion / exclusion data available on the electronic health records
- b. Number and proportion of patients eligible for the intervention
- c. Number and proportion of patients randomised who are sent material from the intervention (letter / sms)
- d. Number and proportion of patients eligible by vaccination status (none, first, second, with booster or without booster)
- e. Number and proportion of patients who opt out for their data to be used or withdraw from the study
- f. Number and proportion of patients who consent for further questionnaires
- g. Number and proportion of patients who are booked for a vaccination appointment
- h. Number and proportion of patients who are categorised a “failed encounter” (not booked, no more action taken)

This list only includes quantitative endpoints in the protocol. There will be additional qualitative analysis of other points in the protocol.

6.2 Timing of outcome assessments

6.2.1 Timing of primary endpoint

Consent and uptake to vaccination will be determined based on patients having the vaccination done. The window to record this will be from the time that the eligible patient in each practice is identified and randomised until 6 months (180 days) follow-up. Follow begins when practices became live, and is the same time for each patient included from the same GP.

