3.2 Randomisation

The practices were randomised in one block by the statistician, independent from the trial team. Individuals within each GP were randomised using simple randomisation in the practice software (reference: <https://learn.microsoft.com/en-us/dotnet/api/system.random?view=net-8.0>). This was done on the same day or shortly after the eligible list was determined. The randomised allocation was concealed to staff; patients were not told about arm beyond option to opt out – where they got the study information from a website.

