6.1 Outcome definitions

6.1.1 Primary outcome

The primary outcome is vaccination uptake in patients individually randomised. This will be measured as the number (percent) of relevant SNOMED codes in eligible patients. Uptake will be measured from the time that the eligible group in each practice is identified (and randomised) until 6 months follow-up (>180 days since randomisation).

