6.3 Analysis methods

6.3.1 Primary analysis

For the primary analysis, uptake of COVID-19 and Flu vaccination will be presented in each arm on an intention to treat basis. The Flu vaccination trial will have both sms and letter group combine as one trial.

We will assess the individual-level-randomised component. This analysis will include all patients who are eligible for the intervention, and who were randomised to receive one of two workflows on an individual basis (standard of care or the PET). All patients from first group of GPs (n=3) in both study periods, and only patients from second group (n=3) who are eligible in the second period (i.e., any eligible patient from first period in the second group of GPs who was vaccinated in the first period would not be part of the analysis sample) will be included. Uptake (from time of randomisation) will be estimated overall. Uptake 95% CIs will be obtained

based on binomial assumption, as well as from a mixed-effects model that allows for hierarchical (random effects) variation by GP. Logistic regression with adjustment described below will be used to estimate the marginal odds ratio of the PET compared with standard of care, and a profile-likelihood ratio confidence interval for the odds ratio will be reported.

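### Section 6.2.1 gives the primary endpoint window two starting points, randomisation and practice go-live, and the SAP does not say that they coincide

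*SAP*

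**What the plan says.** Section 6.2.1 of the SAP describes the window for the primary endpoint in two consecutive sentences. The first runs it "from the time that the eligible patient in each practice is identified and randomised until 6 months (180 days) follow-up". The second says "Follow begins when practices became live, and is the same time for each patient included from the same GP".

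The other sections that define the window use randomisation:

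- 6.1.1 (primary outcome): "from the time that the eligible group in each practice is identified (and randomised) until 6 months follow-up (>180 days since randomisation").
- 6.1.2 item 2 (vaccination rate): "Time is defined as time from randomisation until the earliest of vaccination, leaving the GP, withdrawal the consent of use of data, or death".
- 6.2.2 (3- and 9-month uptake): counted since randomisation.
- 6.3.1 (primary analysis): "Uptake (from time of randomisation) will be estimated overall".

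Two further statements bear on whether go-live and randomisation are the same day. On individual randomisation, 3.2 says "This was done on the same day or shortly after the eligible list was determined". On who is analysed, 6.3.1 includes "All patients from first group of GPs (n=3) in both study periods", while second-group patients enter only if eligible in the second period.

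**The concern.** A programmer who follows the second sentence of 6.2.1 dates every patient's window from one day per practice. A programmer who follows the first sentence, or 6.1.1, dates it from randomisation. If some patients were randomised after go-live, the two programs give different primary results from the same data.

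Absolute uptake is what is exposed. Section 2.2 makes an estimate of uptake, for use in designing the next trial, a secondary objective, and 4.1 reports uptake in each arm with a confidence interval. Balance between arms does not protect that figure.

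Two separate situations could arise, and they act in opposite directions.

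- **Patients who became eligible and were randomised after go-live.** Having not yet been vaccinated is part of eligibility (5.2), so the days between go-live and randomisation hold no countable event. A window fixed from go-live therefore loses that many days of real follow-up, and uptake reads too low.
- **Patients listed at go-live and randomised after a short lag.** A vaccination in the lag could be counted although allocation could not have influenced it. This raises uptake in both arms and slightly dilutes the contrast.

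**Working it through.** The SAP gives no period lengths, randomisation dates or expected uptake that bear on this, so there is no stated figure to reproduce. The check compares the text and then does the window arithmetic under stated assumptions.

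**Step 1: do the two origins coincide?**

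| SAP section | What it implies |
|---|---|
| 3.1 | First-group practices were activated, and their patients randomised, in the first period; compatible with one batch per practice |
| 3.2 | Randomisation on the day of the eligible list or shortly after; a lag is possible |
| 6.1.1 | The practice's eligible group is identified and randomised as a group; compatible with one batch |
| 6.2.1, second sentence | Common start per practice, at go-live |
| 6.3.1 | First-group patients from both periods; either new randomisations in period 2 or continued follow-up of period-1 patients |

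No section says that all patients in a practice were randomised on the go-live day. No section says that any were randomised much later.

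**Step 2: days lost.** For a patient randomised d days after go-live, a 180-day window from go-live contains d days before randomisation and 180 − d days after it.

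**Step 3: uptake for such a patient.** Assume a constant vaccination hazard and true 180-day uptake p. Counted uptake is then 1 − (1 − p)^((180 − d)/180). With p = 30% (assumed):

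| d (days, assumed) | Days after randomisation | Counted uptake |
|---|---|---|
| 0 | 180 | 30.0% |
| 3 | 177 | 29.6% |
| 7 | 173 | 29.0% |
| 30 | 150 | 25.7% |
| 90 | 90 | 16.3% |

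**Step 4: overall uptake when only some patients are late.** Take p = 25% and d = 90 (both assumed). Counted uptake for a late patient is 1 − 0.75^(90/180) = 1 − 0.866 = 13.4%. With a share s of late patients, overall uptake is (1 − s) × 25% + s × 13.4%:

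- s = 10%: 22.5 + 1.34 = 23.8%
- s = 20%: 20.0 + 2.68 = 22.7%
- s = 30%: 17.5 + 4.02 = 21.5%
- s = 0 (one batch at go-live): 25%, no bias

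**Step 5: the arm comparison.** Assume 180-day uptake of 30% against 35%. The odds ratio is (0.35/0.65)/(0.30/0.70) = 1.26. If every patient in both arms were randomised 90 days late, the counted figures would be 16.3% and 19.4%, with an odds ratio of 1.23. At 30 days it would be 1.25. These are extremes, since they put all patients in the late position.

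**Step 6: the vaccination rate.** Section 6.1.2 item 2 starts person-time at randomisation in so many words, so the go-live sentence does not touch it.

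**The case against.** The strongest reply is that the go-live sentence is a description and not a rival rule. Sections 3.1, 3.2 and 6.1.1 fit one list and one randomisation batch per practice. On that reading go-live and randomisation nearly coincide, and the sentence only explains why patients of one practice share a start date. Inclusion from both periods may then mean that period-1 patients are followed through period 2. Section 3.1 makes a parallel statement about which periods contribute data. In addition, 6.1.1 asks for more than 180 days since randomisation, and 3.5 plans a database with more than 180 days of follow-up for all. A truncated window would therefore contradict the outcome definition.

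Much of this stands. The batch reading is plausible, and under it the bias is negligible. It does not remove the contradiction: the SAP never states that randomisation fell on the go-live day, 3.2 allows a lag, and 6.3.1 remains open to new randomisations in period 2.

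A reader might infer more than the text supports:

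- **That uptake will be biased.** This needs late randomisation, which the SAP does not report.
- **That the vaccination rate is biased.** Its time origin is already randomisation.
- **That the late-eligible patients both cannot have an early event and have early events counted.** These belong to different patients, as set out above.
- **That the size is known.** The delay, the share of late patients, the uptake and the hazard are all assumed. A constant hazard is doubtful for seasonal vaccines. If vaccination tends to follow soon after invitation, cutting the end of the window costs less than shown.

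**Conclusion.** The point holds as a contradiction in the definition of the primary endpoint window, with a conditional consequence. Section 6.2.1 states two origins, four other sections use one of them, and the condition under which they agree is nowhere stated.

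If each practice was randomised in one batch at or within a few days of go-live, the choice hardly matters. If some first-group patients were randomised well into the study, a go-live clock would lower absolute uptake in both arms. The loss would be about 1 to 3.5 percentage points on 25% if 10% to 30% of patients were 90 days late, under the assumed constant hazard. The odds ratio would barely move. Any vaccinations counted in a short lag between listing and randomisation would push uptake the other way, by an amount that cannot be worked out from the SAP.

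The correction is worth making because uptake will inform the next trial and the primary window should be codable in only one way.

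**What to change.** In 6.2.1, replace the go-live sentence with wording such as: *Follow-up for each patient starts on that patient's randomisation date and runs a fixed number of days from it; vaccinations dated before randomisation are not events.* If all patients in a practice were in fact randomised on the go-live day, say so as well.

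In 6.3.1, state which meaning of inclusion from both periods applies:

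- new randomisations in period 2, with each patient counted once and from their own randomisation date; or
- continued follow-up of patients randomised in period 1.

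The cost is SAP wording only. The vaccination rate in 6.1.2 item 2 already needs each patient's randomisation date, and 3.5 already plans follow-up beyond 180 days for everyone, so no new data item is needed.

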6.2.2 Timing of secondary endpoints

The number of patients having the vaccination done since randomisation until 3- (90 days) and 9-months (210 days) follow-up.

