3.5 Timing of final analysis

Final analysis will be done by September 2024 using a database with updated follow up (to >180 days for all).

4 Statistical Principals

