6.3.4 Subgroup analysis

Analysis of the primary and secondary endpoints and potential heterogeneity in uptake by subgroups specified below will be undertaken.

- GP
- Deprivation (decile)
- Age group (≥ 18 - < 65 , 65 - < 75 , ≥ 75 y)
- Sex (Male/Female)
- Ethnicity (White, Black, South Asian, Other Asian, Mixed)
- Communication methods for Flu trial (sms, letter)

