6.3.5 Exploratory analysis

We will explore vaccination uptake in patients after 9-months follow-up. We will explore the cluster-randomised component of this study. The population of analysis is those identified as eligible in both groups in the first study period, from the same calendar time. Analysis of uptake will take clustering in the design into account by using generalised linear models with (normal) random intercepts, and the model will also be used to obtain an estimate of the intra-class correlation coefficient. There are several methods to analyse cluster randomised trial data and we will also explore different models and assumptions in order to propose methods for the larger trial.

We will also explore whether a per-protocol analysis would be possible, by determining feasibility to define compliance / contamination from individual randomised allocation using process data. We will explore an analysis that makes use of the comparison between period 1 and period 2 in the n=3 GPs who are activated in the second period. This analysis may be

confounded by temporal effects so is treated as an exploratory analysis.

We will also adjust estimates using additional variables ethnicity and deprivation as an exploratory analysis.

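### The 9-month uptake endpoint is defined at more than 270 days in SAP 6.1.2 but timed at 210 days, which is 7 months, in SAP 6.2.2

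*SAP*

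**What the plan says.** SAP 6.1.2, item 1, defines the secondary uptake outcome: "Vaccination uptake in patients after 3- and 9-months follow-up (>90 and >270 days". SAP 6.2.2, which exists only to time the secondary endpoints, counts patients vaccinated from randomisation "until 3- (90 days) and 9-months (210 days) follow-up".

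The primary outcome has matching day counts in its two places: "until 6 months follow-up (>180 days since randomisation" in 6.1.1 and "until 6 months (180 days) follow-up" in 6.2.1.

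Two further places use the 9-month horizon without giving a day. Item 2 of 6.1.2 is "Mean vaccination rate after 3-, 6- and 9-months follow-up". Section 6.3.5, on exploratory analysis, says "We will explore vaccination uptake in patients after 9-months follow-up".

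**The concern.** One endpoint has two cut-off days in the current text. The section an analyst would naturally consult for the cut-off, 6.2.2, holds the figure that does not fit its own label. Coding from it would give uptake at 7 months under a 9-month heading, only 30 days past the primary window. Estimating uptake to help design the later trial is a stated secondary objective (SAP 2.2), so a mislabelled horizon could be carried forward.

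Two smaller matters follow.

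- The 9-month vaccination rate has no day count of its own, so its horizon has to be inferred from the uptake outcome, where two figures compete.
- Uptake at 9 months is listed as secondary in 6.1.2 and appears again as exploratory in 6.3.5. Section 6.3.4 promises "Analysis of the primary and secondary endpoints and potential heterogeneity in uptake by subgroups specified below will be undertaken", so the label bears on whether subgroup summaries are owed at 9 months. It changes no test and no estimate.

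**Working it through.** **Inputs, all from the SAP**

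| Horizon | Outcome definition | Timing section |
|---|---|---|
| 3 months | >90 days (6.1.2) | 90 days (6.2.2) |
| 6 months | >180 days (6.1.1) | 180 days (6.2.1) |
| 9 months | >270 days (6.1.2) | 210 days (6.2.2) |

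**Step 1: the SAP's month.** 90 / 3 = 30 and 180 / 6 = 30, so the SAP counts 30 days per month.

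**Step 2: can 210 be reproduced as 9 months?** Days = 9 × days per month.

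- 30 days per month: 9 × 30 = 270
- average calendar month of 30.4375 days: 9 × 30.4375 = 273.9
- four-week month of 28 days: 9 × 28 = 252

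None gives 210. The first gives the figure in 6.1.2.

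**Step 3: what 210 days is.** 210 / 30 = 7.0 months, or 210 / 30.4375 = 6.9 calendar months. The SAP defines no 7-month endpoint.

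**Step 4: size of the gap.**

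- 270 − 210 = 60 days, and 60 / 270 = 22% of the 9-month window.
- Beyond the 180-day primary window, 6.2.2 adds 210 − 180 = 30 days where 6.1.2 adds 270 − 180 = 90. The share of added follow-up lost is (90 − 30) / 90 = 67%. This is the same 60 days on a different base, not a second loss.

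**Step 5: could the wording explain it?** The definitions use a greater-than sign and the timing sections give a plain day count. That difference is also present at 3 and 6 months, where the day counts agree, so it cannot account for 60 days.

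No assumption about uptake enters any of these steps.

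**The case against.** The strongest reply is that this is an evident slip with little practical risk. Every mention of the horizon says 9 months, the outcome definition gives 270, and a reader who sets 6.1.2 beside 6.2.2 would notice. The figure belongs to a descriptive outcome in a feasibility study that plans no p-values. This supports a minor rating. It does not remove the contradiction, because a SAP should give one cut-off per endpoint and the wrong figure sits in the section written to provide it.

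Other objections have some weight:

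- **The rate.** Item 2 of 6.1.2 stands directly below the 270-day definition, and 6.2.2 speaks only of the number vaccinated. The natural reading is that the rate also runs to 270 days. The SAP does not say so, but the ambiguity is weaker than for uptake.
- **Secondary or exploratory.** Section 6.3.5 may only mean further exploration of an outcome already listed as secondary. There is no testing hierarchy, so this is a matter of tidying.
- **The 67% figure.** It depends on taking the primary window as the base. The 60 days, or 22%, is the plainer statement.
- **Available follow-up.** Section 3.5 says "Final analysis will be done by September 2024 using a database with updated follow up (to >180 days for all". That is a minimum and does not show that 270 days are lacking. No go-live or extraction dates are given, so no shortfall can be derived.

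**Conclusion.** The contradiction is real and follows from the SAP text alone. On the SAP's own 30-day month, 270 days is the only figure that fits the 9-month label, and 210 days is 7 months. Followed as written, 6.2.2 would cut 60 days (22%) from the window and drop vaccinations on days 211 to 270.

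Severity is minor. The error touches one secondary outcome, with a possible knock-on to the 9-month rate. The 6-month primary outcome and the comparison of arms within GPs are not affected. How far reported uptake would change is unknown, since the SAP gives neither an expected uptake nor its timing. The only inference made is that the 9-month label and the 30-day convention are intended, which every other day count in these sections supports.

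**What to change.** 1. In 6.2.2, change 210 days to 270 days, in line with 6.1.2.
2. State that the 9-month vaccination rate in 6.1.2 uses the same day.
3. Say once whether 9-month uptake is secondary or exploratory, and make 6.1.2 and 6.3.5 agree.

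The cost is one number, one short clarification and one label.

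As a precaution only, check at extraction that every GP has reached 270 days, because 3.5 assures just over 180 and the second group of GPs was activated in a later period (3.1). If any GP has not, restrict the 9-month figure to those that have, or censor at extraction. The check is a comparison of dates for each of the six GPs.

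Optionally, add the horizon day and the extraction date to the events that end person-time for the 3-, 6- and 9-month rates. This is a separate clarification and the correction does not depend on it.

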6.3 Analysis methods

6.3.1 Primary analysis

For the primary analysis, uptake of COVID-19 and Flu vaccination will be presented in each arm on an intention to treat basis. The Flu vaccination trial will have both sms and letter group combine as one trial.

We will assess the individual-level-randomised component. This analysis will include all patients who are eligible for the intervention, and who were randomised to receive one of two workflows on an individual basis (standard of care or the PET). All patients from first group of GPs (n=3) in both study periods, and only patients from second group (n=3) who are eligible in the second period (i.e., any eligible patient from first period in the second group of GPs who was vaccinated in the first period would not be part of the analysis sample) will be included. Uptake (from time of randomisation) will be estimated overall. Uptake 95% CIs will be obtained

based on binomial assumption, as well as from a mixed-effects model that allows for hierarchical (random effects) variation by GP. Logistic regression with adjustment described below will be used to estimate the marginal odds ratio of the PET compared with standard of care, and a profile-likelihood ratio confidence interval for the odds ratio will be reported.

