3.1 Trial design

The PET was designed in qualitative work packages that preceded the feasibility trial. Eligible patients from six general practitioner (GP) practices from Tower Hamlets and Newham were individually randomised 1:1 to the intervention (PET) or control (routine care) during the study. The Appt-Health workflow tool was used, but patients in the control group did not receive additional (individual level) interventions outside routine; however some “cluster-level” interventions were used including posters in surgeries. Letters were used to invite patients with no device to receive SMS invitation for flu vaccination.

To enable a comparison of the intervention to a control group at a practice level, we randomised GPs after they were recruited to the study. n=6 practices were randomised 1:1 to two groups of size n=3 vs. n=3. During a first study period, the first group of n=3 GPs received training, activation of the software, and patients were randomised. This happened for the second group of GPs in a subsequent study period.

A cluster-level analysis will use data from the first period in all n=6 GPs. The individual-randomisation comparison will use data from all GPs, with the second group contributing data from the second period only.

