5.3 Recruitment

Information to be included in the CONSORT flow diagram:

- The location (site),
- Vaccination group (COVID-19, Flu),
- Invitation method (COVID-19: sms; Flu: sms and letter), and
- Study period of each site.

Information on patients assessed for eligibility will not be recorded.

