6.3.2 Adjustments

Adjusted estimates will use:

- GP (categorical)
- Age (continuous)
- Sex (male/female)

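### The primary Flu comparison combines SMS and letter patients but does not adjust for invitation route; adding route, defined in both arms before randomisation, is a small, cheap gain

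*SAP*

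**What the plan says.** Section 6.3.1 combines the two invitation routes for Flu: "The Flu vaccination trial will have both sms and letter group combine as one trial". The arm comparison in the same section reads: "Logistic regression with adjustment described below will be used to estimate the marginal odds ratio of the PET compared with standard of care". Section 6.3.2, under the words "Adjusted estimates will use", lists GP, age and sex. Section 6.3.5 adds ethnicity and deprivation as an exploratory step. Route is in neither set.

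Route does appear elsewhere:

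- Section 3.1 says what determines it: "Letters were used to invite patients with no device to receive SMS invitation for flu vaccination".
- Section 5.3 lists invitation method for the CONSORT diagram, with SMS only for COVID-19 and both routes for Flu.
- Section 6.3.4 includes the subgroup "Communication methods for Flu trial (sms, letter" among those for the primary and secondary endpoints.

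Route is not among the baseline characteristics in section 5.5 or in the dummy table of the Appendix. Section 3.2 describes simple randomisation of individuals within each GP and mentions no stratification by route.

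**The concern.** Patients who cannot receive an SMS are probably different from those who can, and they are reached in another way. If uptake differs between the two groups, route is a prognostic factor. Because randomisation is not stratified by route, the arms may by chance hold different shares of letter patients. The planned model would correct only the part of that imbalance that GP, age and sex happen to capture.

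The definition of route also matters. Section 3.1 defines it by a patient attribute, whereas sections 5.3 and 6.3.4 name it by how the patient was contacted. Controls received no individual-level intervention beyond routine care, so the SAP should say how a control patient is classed as SMS or letter. If route were read from what was sent, the subgroup might not have a like-for-like control group. Device status before randomisation avoids this and serves both the covariate and the subgroup.

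**Working it through.** The SAP gives no sample size (section 3.3 refers to the protocol), letter share or uptake by route, so there is no planned figure to reproduce. All inputs below are assumptions except the 1:1 allocation (section 3.1) and simple randomisation (section 3.2).

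**1. Is there systematic bias?** Let w be the letter share, p_S and p_L the control uptake by SMS and letter, and OR the common conditional odds ratio. The pooled control uptake is p0 = (1−w)·p_S + w·p_L. The pooled PET uptake p1 is the same average after multiplying each route's odds by OR. The odds ratio with route omitted is [p1/(1−p1)]/[p0/(1−p0)].

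- At OR = 1 this is 1.000 in every case tried (p_S = 30%, p_L = 10% to 50%, w = 5% to 50%). There is no bias under the null.
- Example at OR = 1.3, with w = 0.3, p_S = 0.30 and p_L = 0.10: p0 = 0.240 and p1 = 0.7×0.358 + 0.3×0.126 = 0.288, giving an odds ratio of 1.283. Over the whole range the result is 1.277 to 1.298. This is non-collapsibility of the odds ratio, a difference of estimand and not an error.
- Confounding would need allocation to differ by route. With w = 0.2, uptake of 30% and 15%, and 70% of letter patients in the PET arm: p1 = (0.14×0.15 + 0.40×0.30)/0.54 = 0.261, p0 = (0.06×0.15 + 0.40×0.30)/0.46 = 0.280, and a null odds ratio becomes 0.91. The SAP describes nothing of this kind.

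**2. How far can chance imbalance move the estimate?** The SD of the arm difference in letter share is sqrt(4w(1−w)/n). The 95% limit of the shift in the unadjusted uptake difference is 1.96 × SD × d, where d is the uptake gap between routes. For w = 0.2 and d = 0.20:

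- n = 500: 1.96 × sqrt(0.64/500) × 0.20 = 1.96 × 0.0358 × 0.20 = 0.0140, or 1.4 points.
- n = 1000: 1.96 × sqrt(0.64/1000) × 0.20 = 1.96 × 0.0253 × 0.20 = 0.0099, or 1.0 point.

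Range, from w = 0.1 with d = 0.10 to w = 0.3 with d = 0.20:

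| n | Smallest shift | Largest shift |
|---|---|---|
| 500 | 0.053 × 0.10 = 0.5 points | 0.080 × 0.20 = 1.6 points |
| 1000 | 0.037 × 0.10 = 0.4 points | 0.057 × 0.20 = 1.1 points |

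On the odds-ratio scale, with 30% letters and uptake of 30% and 15%, a 1.96-SD imbalance shifts the odds ratio by a factor of about 1.11 at n = 200, 1.05 at n = 1000 and 1.03 at n = 2000.

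**3. Against the width of the interval.** At an assumed 30% uptake, the 95% half-width for the arm difference is 1.96 × sqrt(4×0.3×0.7/n): 8.0 points at n = 500 and 5.7 at n = 1000. Taking out the imbalance component at n = 500 gives sqrt(8.03² − 1.40²) = 7.9 points.

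**4. What adjustment costs in the logistic model.** For p_S = 30%, p_L = 10% to 50%, w = 5% to 50% and OR 1.0 to 1.5, adding route raises the standard error of the log odds ratio by 0.3% to 3.8%. In an extreme case (uptake of 40% and 10%, half letters, OR 1.5) it rises 7.6%, and the odds ratio with route omitted is 1.42. The coefficient moves too: at OR = 1.3 with the largest attenuation, the log odds ratio goes from ln 1.277 = 0.245 to ln 1.3 = 0.262, about 7% larger.

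**The case against.** A reader might infer that combining the routes biases the Flu comparison. It does not: patients are individually randomised 1:1, nothing says that allocation differs by route, and step 1 gives a null odds ratio of exactly 1. A reader might also see a contradiction between combining the routes in 6.3.1 and splitting them in 6.3.4. A pooled main estimate with a pre-specified subgroup is ordinary practice, and the two sections agree.

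The stronger objections concern value. Chance imbalance is sampling error that the 95% interval already covers, and the shifts in step 2 lie well inside the half-widths in step 3. Age adjustment may absorb part of any route effect. GP, age and sex are a defensible short list for a feasibility study without p-values for superiority. In a logistic model adjustment does not shrink the standard error of the coefficient, and it moves the coefficient further from the marginal odds ratio that 6.3.1 names. All of this stands, and it limits the point to a minor one. It does not remove the point: adjustment conditions on the imbalance that actually occurred, and the gap between a conditional coefficient and a marginal target already exists with the three planned covariates.

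It is also fair to say that classification by device status before allocation is inferred from section 3.1 and not stated for controls. That supports writing the definition down. Nothing in the SAP shows that route will be taken from messages sent.

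**Conclusion.** The point holds as a small, optional improvement. The plan neither errs nor contradicts itself by combining the routes. It leaves out a likely prognostic baseline variable that it already needs for its own subgroup, and it does not state how that variable is set in the control arm. The gain is protection against a chance shift of about 1.0 point (n = 1000) to 1.4 points (n = 500) at the 95% limit, assuming 20% letters and a 20-point gap in uptake. Under the other assumptions tried it is 0.4 to 1.6 points, and less after age adjustment. The effect on interval width is slight. If the letter share is very small or uptake is alike in both routes, the covariate will change almost nothing; the definition of route would still be needed for the subgroup.

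**What to change.** - In 6.3.2, add invitation route (SMS or letter) as a covariate for the Flu comparison only. Define it in both arms by device status on the eligible list before randomisation.
- In 6.3.4, state that the SMS/letter subgroup uses the same definition.
- In 6.3.1, state that the marginal odds ratio is obtained by standardising predictions from the adjusted model over the Flu analysis population. The planned profile-likelihood interval belongs to the conditional coefficient, so name a delta-method or bootstrap interval for the standardised odds ratio.

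The cost is one extra parameter, a slightly larger standard error for the conditional log odds ratio, and a few lines of SAP text. The change relies on device status being held for control patients. The planned subgroup already requires this, so it should be confirmed in any case.
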